A patient’s overall/global impression of improvement would be reflective of her overall urinary condition. Although this outcome would seemingly be ideal for capturing a meaningful outcome, for our trial it could potentially introduce bias. Because it is not feasible to mask subjects in ESTEEM to the intervention (BPTx), a single, subjective global impression item would be subject to bias. For example, if subjects in the control group were more likely to ask for additional treatment and report they were not “improved” because they knew there was another potential treatment available that they did not receive, this would bias our study towards a higher failure rate in the control group (making our intervention seem more effective than it really is). The challenges of masking or designing a sham procedure for the control group for ESTEEM have already been noted above (Section 3.2).

3. Problems with using OAB PRO measure as primary outcome

Finally, we considered using an OAB PRO as the primary outcome, such as the Overactive Bladder Questionnaire (OAB-q)⁵⁵ or the UDI-irritative subscale. However, these do not account for SUI symptoms, which are part of the MUI symptom constellation. In addition, it is still unclear whether patients with MUI are at risk of sling failure for SUI and at least 2 studies suggest this may be the case.^{27, 28} Finally, there are some women with MUI who may not be able to clearly distinguish all UI episodes as stress- or urge- related and the team felt it would be important to also capture these symptoms. Finally, specifically regarding the OAB-q, there is less validity data in a MUI population compared to the UDI.

For all of these reasons, using the UDI as the primary outcome is ideal and it has all of the characteristics that are important for a MUI population:

1. The overall UDI score includes both a stress and irritative subscale, allowing us to comprehensively capture both SUI and OAB symptom outcomes.
2. It captures a meaningful outcome from the patient perspective, incorporating both the presence and both of SUI and OAB symptoms.
3. It includes 3 UI items that are not necessarily specific to stress or urge and thus can help capture UI episodes for which patients cannot clearly distinguish as SUI or UUI.
4. It can capture both improvement and worsening of preexisting symptoms, but also the development of new urinary symptoms.⁵⁶

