4.2. Inclusion Criteria

- 1) Presence of both SUI and UUI on bladder diary; and ≥ 2 IEs/3 days
 - a) ≥ 1 Stress IE/3 day diary
 - b) ≥ 1 Urge IE/3 day diary
- 2) Reporting at least "moderate bother" from UUI item on UDI
"Do you usually experience urine leakage associated with a feeling of urgency, that is a strong sensation of needing to go to the bathroom?"
- 3) Reporting at least "moderate bother" from SUI item on UDI
"Do you usually experience urine leakage related to coughing, sneezing, or laughing"
- 4) Diagnosis of SUI defined by a positive cough stress test (CST) or UDE within the past 18 months
- 5) Desires surgical treatment for SUI symptoms
- 6) Urinary symptoms ≥ 3 months
- 7) Subjects understand that BPTx is a treatment option for MUI outside of ESTEEM study protocol (see Section 5.3 for Rationale)
- 8) Urodynamics within past 18 months

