1. Although obstructive symptoms related to prolapse are not a focus of ESTEEM, some items in this subscale may still be relevant to the MUI population (ie: “general urine leakage not related to urge or activity”; symptoms of “difficulty emptying”; and “incomplete emptying”).
2. Because women with symptomatic prolapse will be excluded in both groups, it is unlikely that the inclusion of this subscale in the primary outcome will lead to bias.
3. The published MID for the UDI in the BE-DRI population also includes all 3 subscales for an urge-predominant MUI population.⁵⁰

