Change from baseline in UDI Obstructive Score at 12 months	Continuous	The Urogenital Distress Inventory-Obstructive Score will be computed at baseline and 12 months (and 3 and 6 months) using the standard scoring algorithm. Specifically, the instructions are to average responses across questions E, J, K, L, M, N, O, P, Q, R, and S and their respective sub-questions (0=No or Yes and Not at all; 1=Yes and Slightly; 2=Yes and Moderately; 3=Yes and Greatly), and then multiply by 100/3. If any responses are missing, then the score will be calculated as the average of the non-missing responses. The outcome will then be computed as the difference in score at 12 months (and 3 and 6 months) and the score at baseline. If data for an assessment time point are missing, the outcome variable will be coded as missing.
Exploratory Outcomes		
Change from baseline in Urge Incontinence Episodes at 12 months	Continuous	The daily frequency of urge incontinence episodes will be taken from the bladder diary. The outcome will then be computed as the difference in daily frequency of urge incontinence episodes at 12 months (and 6 months) and the daily frequency of urge incontinence episodes at baseline. If data for the assessment time point are missing, the outcome variable will be coded as missing.
Change from baseline in Stress Incontinence Episodes at 12 months	Continuous	The daily frequency of stress incontinence episodes will be taken from the bladder diary. The outcome will then be computed as the difference in daily frequency of stress incontinence episodes at 12 months (and 6 months) and the daily frequency of stress incontinence episodes at baseline. If data for the assessment time point are missing, the outcome variable will be coded as missing.
Change from baseline in Total Incontinence Episodes at 12 months	Continuous	The daily frequency of total incontinence episodes will be taken from the bladder diary. The outcome will then be computed as the difference in daily frequency of total incontinence episodes at 12 months (and 6 months) and the daily frequency of total

Network

Protocol ESTEEM Statistical Analysis Plan

Variable	Type	Definition
		incontinence episodes at baseline. If data for the assessment time point are missing, the outcome variable will be coded as missing.

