High Voiding Frequency at 12 months	Dichotomous (Yes/No)	
The total number of daytime and nighttime voids will be taken from the bladder diary and summed and divided by the number of diary days (≤ 3) to get a voiding frequency. The indicator for high frequency at 12 months (and 6 months) will be defined for each subject as follows:
 
If > 8 voids/24 hours at time x: Yes If ≤ 8 voids/24 hours at time x: No
 
If data for the assessment time point are missing, the high frequency indicator will be coded as missing.
 
The variable is summarized as the percentage of participants with indicator equal to “Yes” among all non-missing indicators.

Dryness at 12 Months (Diary)	Dichotomous (Yes/No)	
The total number of incontinence episodes will be taken from the bladder diary and summed and divided by the number of diary days (≤ 3) to get an average daily number of episodes. The indicator for dryness at 12 months will be defined for each subject as follows:
 
If 0 episodes/24 hours at time x: Yes If > 0 episodes/24 hours at time x: No
 
If data for the assessment time point are missing, the dryness indicator will be coded as missing. The variable is summarized as the percentage of participants with indicator equal to “Yes” among all non-missing indicators.

Dryness at 12 Months (UDI-LF)	Dichotomous (Yes/No)	
The response to questions C (Do you experience urine leakage related to the feeling of urgency?) and D (Do you experience urine leakage related to physical activity, coughing, or sneezing?) will be taken from the UDI-LF. The indicator for dryness at 12 months will be defined for each subject as follows:
 
If question C = No and question D = No at time x: Yes If question C = Yes or question D = Yes at time x: No
 
If data for the assessment time point are missing, the dryness indicator will be coded as missing. The variable is summarized as the percentage of participants with indicator equal to “Yes” among all non-missing indicators.

Network

Protocol ESTEEM Statistical Analysis Plan

Variable	Type	Definition

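### The exploratory UDI-LF dryness endpoint can code a leaking woman as dry, because it reads only the urge and stress leakage items

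*SAP*

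**What the plan says.** SAP section 9.2 lists three dryness indicators under Exploratory Outcomes. SAP section 13 says they were added at the writing team's request.

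- **UDI-LF version.** Two items are used. The urge item is given as "questions C (Do you experience urine leakage related to the feeling of urgency". The stress item, D, asks about leaking on exertion or with a cough or sneeze. The rule is "If question C = No and question D = No at time x: Yes"; a Yes to either gives not dry.
- **Diary version.** The total number of incontinence episodes is "summed and divided by the number of diary days (≤ 3) to get an average daily number of episodes". Zero is dry and anything above zero is not.
- **Combined version.** Dry only if both of the above are dry.

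Each is coded missing if data for the time point are missing, and each is summarised as a percentage of non-missing values.

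On the content of the UDI, protocol 3.4.1.a gives this as one reason for choosing it: "It includes 3 UI items that are not necessarily specific to stress or urge". It explains that some women with mixed incontinence cannot sort all their leaks into stress or urge. Protocol 6.1.2 defends keeping the obstructive subscale in the total partly because it asks about "general urine leakage not related to urge or activity". In SAP 9.2 that subscale is scored as "average responses across questions E, J, K, L, M, N, O, P, Q, R, and S", so it contains neither C nor D.

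**The concern.** A reader will take dryness to mean no leakage. The UDI-LF version establishes only that a woman reports no leakage she attributes to urgency or to exertion. The protocol expects women in this population whose leaks fit neither label and values the UDI because it captures them, but this indicator drops those answers. The error runs one way: it can turn a leaking woman into a dry one, never the reverse. SAP section 2 says the SAP describes all analyses for the primary manuscript, so the figure may be reported beside the main result.

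The diary version has a smaller problem. Dividing by however many days were kept is reasonable for a mean frequency, and the same phrase serves the voiding-frequency rows. For an all-or-none criterion, each day not kept can only raise the chance of seeing no episode.

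**Working it through.** The documents state no dryness rate or dryness power, so there is no planned figure to reproduce. The check is of the rule itself, followed by illustrations on stated assumptions.

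**1. Items read.** SAP 9.2 assigns A, B, C, G, H, I to the irritative subscale (6), D and F to stress (2), and E and J to S to obstructive (11). 6 + 2 + 11 = 19, which matches the 19-item form in protocol 3.4.1. The dryness rule reads 2 of the 19. The general-leakage item is in the obstructive subscale, so it is among the 17 not read.

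**2. The three rules on women with C = No and D = No.**

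| General leakage item | Episode on a recorded diary day | UDI-LF | Diary | Combined |
|---|---|---|---|---|
| No | No | Dry | Dry | Dry |
| Yes | Yes | Dry | Not dry | Not dry |
| Yes | No | Dry | Dry | Dry |

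The UDI-LF version is wrong in rows 2 and 3, by the rule alone. The combined version is wrong only in row 3.

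**3. Size for the UDI-LF version (assumed inputs).** If a fraction f of the women coded dry report other leakage, the corrected rate is the reported rate × (1 − f). With a reported rate of 40% and f of 5% to 15%, neither of which comes from the documents, this is 40% × 0.95 = 38% down to 40% × 0.85 = 34%.

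**4. Effect on the comparison (assumed inputs).** If a fraction g of non-dry women are coded dry equally in both arms, each rate p becomes p + (1 − p)g and the difference shrinks by the factor (1 − g). With assumed true rates of 40% and 55%, the 15-point difference becomes 14.25 points at g = 5% and 12 points at g = 20%. Equal misclassification raises both rates and dilutes the difference; it does not create one.

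**5. Diary length (assumed inputs).** Protocol 4.2 requires "Presence of both SUI and UUI on bladder diary" with at least 2 episodes in 3 days, so the entry minimum is r = 2/3 per day. For a woman still leaking at that rate, the chance of recording no episode in d days is exp(−rd) under a Poisson model. With gamma variation between women (shape 1) it is 1/(1 + rd).

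| Days kept | Poisson | Gamma variation |
|---|---|---|
| 1 | exp(−0.667) = 51% | 1/1.667 = 60% |
| 2 | exp(−1.333) = 26% | 1/2.333 = 43% |
| 3 | exp(−2) = 14% | 1/3 = 33% |

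A full diary reduces false dry results but does not remove them.

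**The case against.** The best defence is that the UDI-LF row prints the two items it uses, and that these match the trial's definition of mixed incontinence as stress plus urge and the bother items used for entry. On that view the variable is sound and only its name is loose. This stands in part, which is why renaming is an acceptable repair. It does not rescue the name dryness, which the diary row uses for leakage of every type.

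Four stronger readings are tempting and are not supported:

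- *All three endpoints measure only classifiable leakage.* Diary dryness uses total episodes, and protocol 4.3 (criterion 16) shows the diary has a category for other episodes.
- *The three non-specific items can be read off the protocol.* Section 3.4.1.a gives their number but no letters or wording. Only the general-leakage item is described, in 6.1.2, and without its letter.
- *The plan expressly accepts a one-day diary.* This is inferred from an upper limit of 3 days with no lower limit. The planned diary is 3 days. The acceptability check in protocol 4.5 concerns the baseline diary, and nothing shows how often short diaries occur.
- *The arms are misclassified unequally in favour of BPTx.* Only that arm is taught urge and stress strategies, but no data bear on labelling. If the teaching did improve labelling, BPTx would have fewer false dry results, which works against it.

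One might also look to the multiple imputation in SAP 16.2, which covers the dryness indicators. It fills missing values as a sensitivity analysis and cannot correct a value already coded as an observed Yes.

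**Conclusion.** The point holds for the UDI-LF dryness indicator. A woman with C = No, D = No and general leakage = Yes is coded dry by a stated rule, with no assumption needed. The combined indicator has the gap only for leakage that does not fall on a recorded diary day, and the diary indicator does not have it. The missing minimum number of diary days is a separate, secondary weakness.

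The size cannot be determined from the documents: they do not say how many women report only unclassified leakage, how many diaries run short, or whether either differs by arm. The percentages above are illustrations; the 51% in particular applies only to a woman who still leaks at the entry minimum, keeps a single day and follows a Poisson pattern. A reader might infer that the main result is at risk. It is not: these endpoints are exploratory, and the UDI total includes the obstructive subscale that holds the general-leakage item.

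**What to change.** 1. **UDI-LF dryness.** Define Yes as No on C, D and every other UDI-LF item that asks about urine leakage, at minimum the general-leakage item. Take the letters from the form and list them in SAP 9.2. If this is not wanted, rename the variable as no urge or stress leakage.
2. **Combined dryness.** Carry the same rule, or the same renaming, into it.
3. **Diary dryness.** Require a complete 3-day diary and code every shorter diary as missing, whether or not it records a leak. Keeping a leak on a short diary as not dry while setting only leak-free short diaries to missing looks natural but should be avoided. Short diaries could then contribute only No to a percentage taken among non-missing values, so their dry rate would be 0% by construction. The imputation in SAP 16.2 would not repair the main summary.

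The cost is SAP wording and a recode of items already collected. The stated dry rate will fall or stay the same under change 1, and change 3 will add some missing diary values.

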Dryness at 12 Months (UDI-LF and Diary)	Dichotomous (Yes/No)	
The responses to Dryness at 12 Months based on the UDI-LF and the diary will be combined. The indicator for dryness at 12 months will be defined for each subject as follows:
 
If Dry (Diary) = Yes and Dry (UDI-LF) = Yes at time x: Yes
 
If Dry (Diary) = No or Dry (UDI-LF) = No at time x: No
 
If data for the assessment time point are missing, the dryness indicator will be coded as missing. The variable is summarized as the percentage of participants with indicator equal to “Yes” among all non-missing indicators.

Change from Baseline OAB-q Symptom Severity Score at 12 Months	Continuous	
The OAB-q Symptom Severity Score will be computed at baseline and 12 months (and 3 and 6 months) using the standard scoring algorithm. Specifically, instructions are to sum responses across questions 1 through 8 (1= Not at all, 2=A little bit, 3=Somewhat, 4=Quite a bit, 5=A great deal, 6=A very great deal), then subtract the minimum possible score (8) and divide by the range of possible score (48-8=40), then multiply by 100. If less than half of the responses are missing, then the score will be calculated by substituting the missing responses with the average of the non-missing responses, otherwise no score is calculated. The outcome will then be computed as the difference in score at 12 months (and 3 and 6 months) and the score at baseline. If data for an assessment time point are missing, the outcome variable will be coded as missing.

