16.2 Missing Data and Multiple Imputation

Sensitivity analysis to see the impact of missing data on the primary outcome (UDI Total score) and the dryness and MID indicators will be performed using multiple imputation. Missing data at 3, 6, and 12 months will be imputed using non-missing data from prior time points (including baseline) to inform the imputed values as well as age, treatment, race, ethnicity, BMI, smoking status, estrogen use (oral/patch), site, incontinence episode group (from randomization), vaginal delivery count, and private insurance indicator. Missingness will first be assured to monotone missing (i.e. ensure not missing prior time points when later time points are present) 25 times using MCMC methods, then all other missing data will be imputed for each of the 25 monotone-missing datasets using regression and logistic imputation methods. Each imputed dataset will be fit using the models described in Section 9.3. Differences between groups for each imputed dataset will then be combined to estimate average effects and standard errors and compared to the model without imputation. All imputation will be performed using SAS v9.4.

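### As literally written, the exploratory UDI-LF and combined dryness rules keep partly observed leakers as not dry but drop partly observed dry women, so both percentages come out too low unless the missing-data sentence overrides

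*SAP*

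**What the plan says.** SAP 9.2 defines three dryness indicators at 12 months and lists them with the exploratory outcomes.

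- **Diary.** Episodes are "summed and divided by the number of diary days (≤ 3) to get an average daily number of episodes". Zero is dry and anything above zero is not. No minimum number of diary days is given.
- **UDI-LF.** Dry: "If question C = No and question D = No at time x: Yes". Not dry: "If question C = Yes or question D = Yes at time x: No".
- **Combined.** Dry: "If Dry (Diary) = Yes and Dry (UDI-LF) = Yes at time x: Yes". Not dry: "If Dry (Diary) = No or Dry (UDI-LF) = No at time x: No".

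All three carry the same closing text: "If data for the assessment time point are missing, the dryness indicator will be coded as missing", and then "The variable is summarized as the percentage of participants with indicator equal to “Yes” among all non-missing indicators".

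Attachment 16.2 plans multiple imputation as a sensitivity analysis for UDI Total and for the dryness and MID indicators. Its predictors are earlier visits and a list of baseline characteristics: "Missing data at 3, 6, and 12 months will be imputed using non-missing data from prior time points". The other dryness component at the same visit is not listed. SAP 13 records that the dryness endpoints were added at the writing team's request.

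**The concern.** With complete data, the 'and' line and the 'or' line are exact complements and nothing is wrong. With one component missing they are not. A single wet component satisfies the 'or' line and fixes the answer as No. A single dry component satisfies neither line. Because the percentage uses non-missing indicators only, partly observed leakers stay in the denominator and partly observed dry women leave it. That selects on the outcome itself, so it biases the rate even when the missingness is unrelated to anything.

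The closing sentence on missing data does not settle the matter. It does not say whether one absent component triggers it, or whether it takes precedence over the 'or' line. Elsewhere SAP 9.2 is explicit about partial data: UDI Total is not calculated if a subscale is missing, and the OAB-q scores have a less-than-half-missing rule. The dryness rules have no counterpart.

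At stake is the accuracy of two exploratory percentages that patients and clinicians read easily. If diary return differed by arm, the comparison between arms would be affected as well.

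**Working it through.** The documents state no dryness rate, diary-return rate or item-missing rate, so there is no plan figure to reproduce. All rates below are assumptions.

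**1. Trace of the combined rule.**

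| UDI-LF | Diary | Lines as written | If any missing component means missing |
|---|---|---|---|
| dry | dry | Yes | Yes |
| wet | observed | No | No |
| dry | wet | No | No |
| wet | missing | **No** | missing |
| dry | missing | **no line fits, drops out** | missing |
| missing | wet | **No** | missing |
| missing | dry | **no line fits, drops out** | missing |

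The UDI-LF rule has the same structure, with items C and D as the two components.

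**2. Size for the combined indicator.** Let p be the true share dry on both, pU the true share dry on the UDI-LF, and m the share of women with a UDI-LF result but no diary, missing completely at random. Then

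reported rate = (1−m)p / [(1−m) + m(1−pU)].

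With p = 0.38, pU = 0.45 and m = 0.10: 0.90×0.38 / (0.90 + 0.10×0.55) = 0.342/0.955 = 35.8%.

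| True p / pU | m = 5% | 10% | 15% | 20% |
|---|---|---|---|---|
| 20% / 30% | 19.3 | 18.6 | 17.8 | 17.0 |
| 30% / 35% | 29.0 | 28.0 | 26.9 | 25.8 |
| 38% / 45% | 36.9 | 35.8 | 34.6 | 33.4 |
| 45% / 55% | 44.0 | 42.9 | 41.7 | 40.4 |
| 50% / 65% | 49.1 | 48.1 | 47.1 | 46.0 |

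The fall is about 1 point at 5% missing. At 15–20% it is about 3 to 5 points on the middle rows, and 2.2 to 4.6 over the whole table.

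**3. Arm difference, only if diary return differs.** With equal true dryness of 38%, 5% missing in one arm against 15% in the other gives 36.9 − 34.6 = 2.3 points. Against 20% it gives 36.9 − 33.4 = 3.5 points. With equal m in both arms and equal true rates the difference is zero.

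**4. Size for the UDI-LF indicator.** Let each item be blank independently with probability i, and let pC and pD be the shares answering No to C and D. Then

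reported rate = (1−i)p / [(1−i) + i(2−pC−pD)], with p now the share answering No to both.

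With p = 0.40, pC = 0.50, pD = 0.65 and i = 0.05: 0.38/(0.95 + 0.05×0.85) = 0.38/0.9925 = 38.3%, a fall of 1.7 points. Here 2×0.05×0.95 = 9.5% of women have exactly one blank. At i = 0.01 the fall is 0.3 points.

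**5. What imputation does.** At m = 0.10 in the 38%/45% case, the omitted women are 0.10×0.45 = 4.5% of the total, and their true rate of being dry on both is 0.38/0.45 = 84%.

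- Imputed at the observed average, the result stays at 35.8%.
- Imputed at an illustrative 60%, it is 0.342 + 0.045×0.60 = 36.9%.
- Imputed at 84%, it is 0.342 + 0.038 = 38.0%.

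The repair therefore depends on how well the model knows that these women are UDI-dry.

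**6. The diary-only indicator.** A wholly missing diary is simply missing, so there is no asymmetry. A short diary errs the other way. With a per-day dry probability of 0.8 and independent days, the chance of being coded dry is 0.512 on three days, 0.640 on two and 0.800 on one. If 10% of diaries have two days, the rate is 0.9×0.512 + 0.1×0.640 = 0.525, or +1.3 points. If that 10% have one day, it is 0.541, or +2.9 points. This also pushes the combined indicator upward.

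**The case against.** The strongest reply is that the closing sentence already covers a missing component. On that reading, both indicators are missing whenever either part is absent, and there is no bias under missingness completely at random. The reading is available. But the text does not state it, and it would contradict the 'or' line for a woman with one observed leak. What stands is that the bias depends on an unresolved precedence. It is not certain to occur.

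Four stronger inferences are tempting, and the documents do not support them.

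- **All the dryness rules work against dry women.** They do not. The diary-only indicator accepts one or two dry days as dry and can overstate dryness. Because this feeds the combined indicator, the net direction there depends on how common short and missing diaries are.
- **Missing diaries distort every dryness endpoint in this way.** A missing diary cannot affect the UDI-LF indicator, and it only removes a woman from the diary-only one. The diary argument concerns the combined indicator.
- **The effect favours BPTx, because diary review is part of that intervention** (Protocol 5.4, Table 10). BPTx sessions end at 6 months, the 12-month diary is scheduled for all subjects (SAP 4.6), and controls keep diaries at the same intervals (Protocol 5.3). No document shows unequal return at 12 months.
- **Imputation leaves the problem untouched.** Earlier UDI data inform the imputation and would probably recover part of the loss. The no-recovery figure in step 5 is the limiting case. Imputation is, however, a sensitivity analysis and does not change the main reported percentage.

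It is also fair to say that the stakes are modest. These endpoints lie outside the three hypotheses tested at 0.05 in SAP 7.7.

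**Conclusion.** The point holds for the UDI-LF and combined indicators. Coded as written, they retain partly observed leakers and discard partly observed dry women. Taken alone, this understates the combined rate by about 1 point at 5% missing diaries and about 3 to 5 points at 15–20%. It understates the UDI-LF rate by about 0.3 points at 1% and 1.7 points at 5% per-item missingness. These sizes rest on assumed dryness rates, independence of missingness from outcome, and the 'or' line prevailing over the missing-data sentence.

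A false arm difference is conditional on unequal diary return, so it is a vulnerability and not a finding. Because the endpoints are exploratory, this is a correction worth making to the definitions. It does not touch the trial's main conclusions.

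**What to change.** **In SAP 9.2,** set the UDI-LF indicator to missing unless C and D are both answered. Set the combined indicator to missing unless both component indicators are observed. Under missingness completely at random the combined rate becomes (1−m)p/(1−m) = p, whatever m is in each arm.

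**In SAP 16.2,** impute the UDI-LF and diary dryness components using each other at the same visit as well as prior visits, and then derive the combined indicator. A woman with an observed leak then stays not dry, and a UDI-dry woman has only her diary result imputed.

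The cost is a few sentences and a few lines of code. The observed-case table for the combined indicator loses the partly observed leakers: in the 38%/45% case at 10% missing diaries, 0.10×0.55 = 5.5% of women with a UDI-LF result. The derived imputation restores them as not dry.

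This does not address the upward pull of short diaries. SAP 9.2 should also state the minimum number of diary days needed to code a woman as dry.
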